Secondary impacts of proposed research: The reported quality metrics could potentially contribute to ongoing professional practice evaluations (OPPE), which we will evaluate during the trial. Measurement of completeness (i.e. cecal intubation rate) and inspection quality (i.e. ADR) of colonoscopy is a recommended part of OPPE for VA endoscopists, and emphasizes to VA providers that VA values high quality procedures for Veterans. However, current data limitations and the time burden for manual data collection and processing are major impediments to providing and tracking accurate performance data to incorporate into OPPEs. **The reporting of quality measures will also improve access to care.** Colonoscopies with poor bowel preparation result in canceled procedures or repeat procedures at earlier intervals (e.g. 1 year). More repeat procedures leads to decreased access to endoscopy specialty care for new patients. If VA could identify and highlight high quality endoscopy centers and endoscopists, that data could be used to promote system wide improvement, protocol and documentation standardization, and adoption of best practices to ensure access to high quality colonoscopy for all Veterans.

Audience for research results and how they will use the products: VA-EQuIP will have multiple primary and downstream users and stakeholders including:

- The VA National Gastroenterology Program Office as noted above, the sponsor of VA-EQuIP.
- The Office of Specialty Care and Primary Care to ensure Veterans are referred to high quality providers.
- The Office of Veterans Access to Care (OVAC) and National GI Access initiative to ensure that access initiatives are aligned on providing Veterans with high quality procedures.

The proposal directly addresses VA priorities by system modernization and efficient use of resources.

1. “Modernize our systems”: National standardized colonoscopy quality reporting will improve infrastructure and streamline services by providing accurate, prospective quality monitoring that currently does not exist.
2. Focus resources more efficiently: The manual chart review used by most sites to capture quality metrics results in significant unaccounted work burden across the VA healthcare system. VA EQuIP will make this inefficient practice obsolete.

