We created an operational database of colonoscopy procedures and linked pathology notes housed in the VA CDW Text Integration Utility that can be semi-automatically updated with the most current data across the VA healthcare system. We have optimized a machine learning document classifier that uses the support vector machine algorithm to delineate a note as either a colonoscopy procedure note, or not. Our process allows to rapidly and prospectively confirm colonoscopy notes for NLP processing and colonoscopy quality reporting. Our NLP pipelines to extract colonoscopy procedure and pathology data have excellent performance (Table 1). The VA-EQuIP dashboard visually presents biannual and cumulative colonoscopy quality metrics to VA sites and providers, and provides comparison metric data at the local site and national level (Figure 2). All reports are created using Microsoft™ SQL Server Reporting Services 2013 and are hosted on a Microsoft SharePoint 2013 internal website. Access is controlled by both SharePoint memberships and local data access permissions.

Usability and [Pilot] Testing: In cooperation with our operations sponsor and partner, we obtained feedback and usability information on VA-EQuIP from the GI Field Advisory Committee. The committee members were provided access to their sites and individual data on colonoscopy quality. Respondents (N=5) provided feedback for internal consistency and were surveyed via the System Usability Scale (SUS).⁴⁹ The average SUS score for VA-EQuIP for 5 respondents was 87.0 (SD 9.9, range 77.5-100). A score >80.3 has been found to be in the top 10% of usability performance based on an ev

Table 1: NLP Performance for Colonoscopy Quality Metrics

Variable	PPV	Sensitivity	F Measure
ADR	98%	100%	99%
Screening Indication	89%	100%	94%
Cecal Intubation Rate	98%	99%	99%
Bowel Prep Adequate	100%	100%	100%

ates for NLP processing and colonoscopy quality reporting. and pathology data have excellent performance (**Table**

Facility Name:North Hospital **Provider Name:** Dr. C **Report Year:** 2017

[figure not shown]

Figure 2: VA-EQuIP Quality Dashboard

RESEARCH OVERLAP

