[Analysis Overview: Our goal is to compare the efficacy of VA-EQuIP versus usual care for the primary outcomes of overall (all indications) and screening indication ADR and secondary outcomes of bowel preparation quality and cecal intubation rate. We hypothesize that VA-EQuIP will lead to a higher rate of ADR, bowel preparation quality and cecal intubation relative to standard of care. We also hypothesize the effect will be particularly pronounced among providers who have low ADR, bowel preparation quality and cecal intubation rates prior to our intervention. The primary analysis takes advantage of the stepped wedge design by simultaneously comparing pre- and post- intervention data both within and across providers to evaluate the effect of the intervention while controlling for secular trends, which are uniform across sites. As a secondary analysis, we will implement a two-stage interrupted time-series and meta-regression analysis, which is commonly used to study intervention effects when an intervention occurs at different times within different providers. For all analyses, our primary inferences evaluate the ratio of ADR with versus without intervention for a given provider. However, our planned analyses also address the data structure, which nests patients within providers within sites.]

Eligibility / Inclusion criteria: We have identified 73 VA sites spanning VA (**Figure 4**) eligible for the study that have endoscopists with colonoscopy procedure and pathology notes in our database (SCS_Endoqual). In 2017, these 73 sites had 657 providers performing 155,926 colonoscopy procedures. The point of contact (i.e. GI section chief) at each site will be contacted by email about planned VA-EQuIP implementation and given specific instructions for accessing site data.

Exclusion criteria: VA facilities without existing colonoscopy procedure or pathology notes in our operational database will not be included in the study.

Consent: The national GI program office will implement VA-EQuIP as an operational initiative. We will obtain provider verbal consent by telephone, if deemed necessary by the IRB, for the evaluation.

Figure 4: VA-EQuIP sites

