Colonoscopy quality report card & reporting infrastructure: The VA-EQuIP quality reporting infrastructure includes 2 separate CDW databases with an extract, transform, loading (ETL) framework and secure SharePoint Site to visually present quarterly colonoscopy quality metrics (**Figure 2**). VA-EQuIP has been pilot tested and undergone iterative usability testing with the Gastroenterology Field Advisory Committee.

Data measures: CDW structured data include patient demographics and endoscopist name and specialty (e.g. gastroenterology, surgery). Variables derived from natural language processing of colonoscopy procedure and pathology notes include extent of exam, screening indication, and adenoma detection.

Outcome measures: The primary outcomes are overall and screening ADR for endoscopists after implementation of the quality report cards, [with an average follow up of 19.5 months (range 12-27 months).] Overall ADR is defined as the percentage of patients undergoing colonoscopy for any indication with one or more adenomas detected. Screening ADR is defined as the percentage of patients ≥ 50 years undergoing screening colonoscopy who have one or more adenomas detected. We will assess secondary outcomes measures, including cecal intubation rate and bowel preparation quality. Cecal intubation is defined as passage of the colonoscopy tip to a point proximal to the ileocecal valve so that the entire cecum is visible. The cecal intubation rate is the proportion of colonoscopies with cecal intubation documented in the procedure note. Bowel preparation quality is determined by the endoscopist for bowel cleanliness allowing polyp visualization and removal.

Primary Analysis -- Stepped Wedge at the Provider Level: We will utilize patient data aggregated to the provider level at monthly intervals to examine how the ADR changes pre- and post-intervention. A provider's monthly ADR is the ratio of the total number of the provider's positive ADR screening results to the total number of patients that the provider screened during the month. Prospective data collection will begin Jan 1st, 2020 and conclude Jun 30, 2022, a 30-month data collection period. Baseline data from 2019 will be included in our analysis to augment the pre-intervention time frame, to enable our intervention to start immediately. ADR

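### The cecal intubation outcome counts documented intubations, and the intervention feeds note-derived metrics back to the note writers, so a rise at crossover could reflect fuller notes instead of more complete examinations

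*Combined protocol and SAP*

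**What the plan says.** Under Aim 1, Outcome measures, cecal intubation is first defined as a physical event: "passage of the colonoscopy tip to a point proximal to the ileocecal valve". The rate is then scored from the record: "The cecal intubation rate is the proportion of colonoscopies with cecal intubation documented in the procedure note". The data source is note text: "Variables derived from natural language processing of colonoscopy procedure and pathology notes include extent of exam, screening indication, and adenoma detection". No rule is given for a note that is silent on extent.

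The Analysis Overview names "secondary outcomes of bowel preparation quality and cecal intubation rate" and hypothesizes that "VA-EQuIP will lead to a higher rate of ADR, bowel preparation quality and cecal intubation relative to standard of care".

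On feedback, the section on the quality monitoring system says: "The VA-EQuIP dashboard visually presents biannual and cumulative colonoscopy quality metrics to VA sites and providers". Table 1 in that section lists the cecal intubation rate among the extracted metrics (PPV 98%, sensitivity 99%). Table 2 has dashboard links emailed to stewards and providers at T(0). The section on secondary impacts says the metrics may contribute to professional practice evaluations, and names cecal intubation rate as a recommended component of them.

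On preparation, Outcome measures says: "Bowel preparation quality is determined by the endoscopist for bowel cleanliness allowing polyp visualization and removal".

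The planned quality check, in the section on pitfalls and alternative plans, compares extraction output with manual annotation of a sample of the same notes. It measures precision only, unless the system has to be adapted.

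**The concern.** The definition mixes two quantities: whether the cecum was reached, and whether the note says so. The intervention can act on both. A provider shown a low rate can raise it by examining more completely or by recording the landmark more consistently, and the second is easier. A possible link to professional evaluation adds a motive.

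Any change in recording would start when a site crosses over, because the dashboard prompts it. The pre/post indicator in the primary model would therefore absorb it. Calendar-quarter terms and concurrent control sites remove trends common to all sites, not a change that the intervention causes. The interrupted time-series and patient-level analyses would use the same note-derived outcome and inherit the problem. The validation shows whether the note was read correctly; it cannot find an intubation that was performed but not written down.

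What is at stake is the secondary hypothesis. A positive result for cecal intubation could not be read as more complete examinations. Bowel preparation is exposed in a related way, since the endoscopist receiving feedback supplies the rating.

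**Working it through.** The plan states no baseline rate, effect size or power for cecal intubation, so there is no figure of its own to reproduce for this outcome.

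**1. Effect of documentation alone.** Let *t* be the true intubation rate and *d* the share of complete examinations whose note says so. Then measured rate = *t* × *d*. Both values are assumptions. With *t* constant at 0.95:

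| *d* before → after | Measured rate before → after | Change | Ratio |
|---|---|---|---|
| 0.97 → 0.98 | 0.9215 → 0.9310 | +0.95 points | 1.010 |
| 0.95 → 0.98 | 0.9025 → 0.9310 | +2.85 points | 1.032 |
| 0.90 → 0.98 | 0.8550 → 0.9310 | +7.6 points | 1.089 |

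The ratio equals *d* after / *d* before, whatever the constant *t*.

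**2. Could such a shift be declared an effect?** Inputs from the Power Calculation are 69 sites, 571 providers, 59 patients per provider per quarter and ICC 0.030. This gives 59 × 571 / 69 = 488 patients per site per quarter. I assumed two-sided alpha 0.05, six waves and the Hussey-Hughes stepped-wedge variance. As a check on the set-up, the stated ADR power (about 93% for 27.5% to 28.5%) comes out at 92.4% with 10 quarters and 93.3% with 11.

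The same set-up with 10 quarters, at an assumed measured rate of 90%, gives:

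| Purely documentary shift | Power, binomial variance | Power, Poisson variance |
|---|---|---|
| 0.5 points | 71% | about 13% |
| 1 point | over 99% | about 37% |
| 2.85 points | over 99% | over 99% |

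The Poisson column sets the within-site variance to *p* instead of *p*(1 − *p*), since the primary model is Poisson; the plan writes out no separate model for this outcome. Small shifts are therefore not certain to be significant, but a shift near 3 points would be detected under either variance.

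**3. Which denominator separates the two effects?** Hold *t* at 0.95 and assume incomplete examinations are always stated as such.

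| *d* | Documented reached / all | Explicitly short / all | Not stated / all | Short / notes stating an extent |
|---|---|---|---|---|
| 0.90 | 85.50% | 5.00% | 9.50% | 0.05/0.905 = 5.52% |
| 0.95 | 90.25% | 5.00% | 4.75% | 0.05/0.9525 = 5.25% |
| 0.98 | 93.10% | 5.00% | 1.90% | 0.05/0.981 = 5.10% |

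With all colonoscopies as the denominator, the explicitly incomplete share does not move when only documentation changes. Restricting to notes that state an extent keeps the artifact: the ratio is 5.10/5.25 = 0.971 for 0.95 to 0.98, and 5.10/5.52 = 0.923 for 0.90 to 0.98.

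**The case against.** The strongest reply is that nothing shows the bias will occur. The documents give no baseline documentation rate, and if nearly all notes already record extent, little room is left for it. Display of this particular metric to providers is inferred from Table 1 and the section on secondary impacts, because the dashboard figure is not available. How silent notes are scored is implied by the definition, not stated. The collaborative learning content in Table 2 covers preparation protocols, polyp identification and technique, not note-writing. The steward surveys ask about changes in measurement, reporting and technique, which gives some site-level evidence on what changed. These are also secondary outcomes.

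All of this limits the size and certainty of the problem. It does not remove it: the surveys do not measure note completeness, and no planned analysis in the document as supplied tests for a change in recording.

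Three stronger readings are tempting but unsupported.

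- A reader might infer that the protocol expects "protocol and documentation standardization" to follow from the feedback. That phrase describes what the data could be used to promote if high-quality centers were identified. It is conditional and system-level, and does not predict how providers will respond in the trial.
- A reader might infer that the rate will rise after crossover. The documents support only that it could.
- A reader might infer that, with more than 130,000 procedures a year, any small recording change would be significant. That ignores clustering, and the power figures above show that it depends on the shift and the variance model.

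**Conclusion.** The point holds as a risk to interpretation. As defined, the secondary outcome cannot distinguish more complete examinations from more complete notes, and neither the design nor the planned validation separates them. The size is unknown. Under an assumed constant true rate of 95%, the artifact ranges from about 1 point (documentation 97% to 98%) through 2.9 points (95% to 98%) to 7.6 points (90% to 98%), and would be close to zero if baseline documentation is already near complete. The conclusion rests on the plain reading that silent notes count as failures, and on the cecal intubation rate being among the metrics fed back. It does not extend to the primary outcome in the same degree, since ADR also draws on pathology notes. For bowel preparation the exposure is related but partly different: a more generous rating by the audited endoscopist is not a documentation gap.

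**What to change.** Before the secondary outcomes are analyzed, amend the analysis plan as follows.

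1. From the extent-of-exam variable, classify every colonoscopy as cecum reached, explicitly short of the cecum, or extent not stated.
2. Estimate the intervention effect on the explicitly incomplete share and on the not-stated share, each with all colonoscopies as the denominator, not only notes that state an extent.
3. Keep the present rate, labeled *documented cecal intubation*.
4. Claim more complete examinations only if the explicitly incomplete share falls and the not-stated share does not rise. Set a small margin for the second condition in advance, because a real gain at constant documentation lifts the not-stated share slightly: with *d* = 0.95 and *t* rising from 0.95 to 0.97, it goes from 0.95 × 0.05 = 4.75% to 0.97 × 0.05 = 4.85%.
5. Report the not-stated share for bowel preparation by period. State as a limitation that the rating comes from the audited endoscopist, which this step does not remove.

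The cost is a few extra model fits, and possibly a smaller headline secondary effect. It also needs a check that the extraction output separates notes truly silent on extent from missed text. The planned validation measures precision only, so some recall checking would have to be added, and the documents do not confirm that a three-level variable is already stored.

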We will construct a mixed effects generalized linear model that will act on data aggregated monthly within each provider to estimate the average intervention effect across providers. We will use a Poisson outcome model with a log link to characterize each provider’s monthly rate, where the number of positive screens will be the outcome and the log of the number of total screens will be included as an offset term.^{53,54} In the case of over-dispersion, we will use a negative binomial outcome model. The main predictor of interest will be a pre/post indicator for whether the report card intervention was in effect at a particular month (Intervention). We will additionally control for time since the study began in quarters (Time, coded as a categorical variable) to account for secular trends; as well as site level characteristics obtained from administrative and the quantitative survey data (Aim 1) (urban/rural, cumulative annual procedure volume in 2018 and current volume, site annual ADRs in 2018, use of split dose bowel preparation protocols (SDBP) in 2018, and whether or not ADR was measured in 2018), provider level characteristics (baseline years in practice, primary practice type {academic, hospital employed, private practice}, and baseline annual procedure volume), and baseline patient characteristics aggregated to the provider level (age, sex, race/ethnicity). Since study time will be coded in quarters, it will incorporate seasonal effects in addition to secular trends over the study period. Random effects will be included for both provider and site, where provider is nested within site. Let $PositiveScreens_{ijt}$ denote the observed number of positive screens for the j th provider at site i during month t , and let $TotalScreens_{ijt}$ denote the total number of patients screened. Because the monthly screening rates are expected to be relatively low (≤ 0.30), we assume that the observed number of positive screens, $PositiveScreens_{ijt}$ follows a Poisson distribution with conditional mean λ_{ijt} . We anticipate the following model for λ_{ijt} on a log scale, where $TotalScreens_{ijt}$ is included as an offset term on the right hand side of the equation: $\text{Log}(\lambda_{ijt}) = \beta_0 + \beta_1 Intervention_{ijt} + \beta_2 Time_{ijt} + \beta_3 Urban_i + \beta_4 SiteVolume_i + \beta_5 YrsPractice_{ij} + \beta_6 PracticeType_{ij} + \beta_7 ProviderVolume_{ij} + \beta_8 Age_{ij} + \beta_9 Sex_{ij} + \beta_{10} Race_{ij} + \beta_{11} Volume2018_i + \beta_{12} ADR2018_i + \beta_{13} SDBP2018_i + \beta_{14} ADRMeasured_i + \alpha_i + \mu_{j(i)}$, where β_0 is the intercept, β_2 is a vector of coefficients for the study quarter as expressed by $Time_{ijt}$, α_i indicates the random effect for site i , $\mu_{j(i)}$ indicates the random effect for provider j within site i . $Volume2018_i$ (high/low), $ADR2018_i$ (high/low) and $ADRMasured_i$ (yes/no) are the indicator variables used in stratifying the baseline randomization of sites to waves. We will also examine whether the intervention effect varies by time since intervention and by provider characteristics by considering these interaction terms in the model. Under the proposed Poisson model and logarithmic link function, exponentiating the results will allow us to report rate ratios (RRs), their 95% confidence intervals (CIs), and p-values from the models. Under the generalized linear mixed model the estimated treatment effect, obtained by exponentiating the estimate of β_1 , represents the ratio of the screening rate after versus before implementing the intervention for a given provider.

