
We will plot monthly ADRs for a random sample of endoscopists to examine how the ADR rate changes over time, and to check for the presence of a lagged intervention effect. We expect to see about a one month lag in the intervention effect and plan to drop the outcome data for this period to avoid biased estimates.⁵⁵ We will

examine correlation between successive monthly ADR rates within providers using residual plots and the Durbin-Watson or Durbin's alternative test and include study time lags as appropriate.⁵⁶ If these analyses suggest that the residual covariance deviates substantially from those assumed by the nested random effects model, we will substitute a generalized estimating equation (GEE) analysis under the assumption that outcomes are independent between sites, and use robust standard errors for statistical inference.⁵⁷ The GEE approach can also be used as a fallback if the nested random effect structure of the generalized linear mixed model turns out to be numerically intractable. [As a secondary question we will assess the impact of compliance with the intervention on ADR rate among the providers from Aim 2 who responded to our survey. Compliance will be measured in Aim 1 by dashboard access and participation in one or more collaborative learning sessions. Compliance will be modeled as an interaction with intervention in the model described above, to see if the efficacy of the intervention varies by compliance status.]

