Power Calculation: Our power calculation for the intervention effect comes from a stepped wedge model. Based on 2017 data there were 73 sites with 657 providers performing 155,926 cases per year in our sampling frame. We estimate a 5% loss of site data due to data quality issues. We also estimate a provider attrition rate of 8% from four years of data provided by the national GI program office where attrition rates ranged from 6.9-12%.¹⁵ After accounting for data loss and provider attrition, we expect 69 sites with 571 providers seeing 135,517 patients/year, corresponding to 95 providers/wave and 59 patients/provider/quarter. Note that the number of patients seen by providers factors into our power calculation as it affects the standard errors of the intervention effect, where seeing more patients yields greater power. Our primary outcome is ADR, which we will conservatively estimate as having a range of 13-79% based on prior research^{7,8} and our preliminary data. For cluster randomized trials using implementation designs such as ours, the intra-cluster correlation coefficient (ICC) estimates for patient outcomes are approximately 0.030.⁵⁸ Based on an ADR of 27.5% in the pre-intervention period, we would have about 93% power to detect a 1.0% absolute increase in ADR. This difference is clinically important, because a 1% increase in ADR is associated with a 3.0% decrease in risk of incident CRC, and a 5% decrease in risk of fatal interval CRC.⁷ Power calculations were conducted in R using the swCRTdesign package, and are conservative due to exclusion of three quarters of baseline data, and because the second level of clustering by provider is not considered.^{59,60}

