Quantitative Survey Design and Qualitative Interview Guide: [Our quantitative surveys for quality stewards and individual providers include measures we have defined for each domain. Surveys will be delivered pre- and post (12 months) VA-EQuIP implementation; interviews will be conducted after each randomized cluster through trial completion.] A full description of all data sources, measures, outcomes, quantitative surveys, and qualitative interview guide are available in **Appendices 5-8**. We have developed draft survey questionnaires for quality stewards [and providers and a provider interview script to capture the intended constructs of our conceptual framework.] Because our measures are specific to the VA-EQuIP intervention, it was necessary to develop specific questionnaire items with our co-investigator and survey design expert [name]. Development has been an iterative process, wherein all necessary constructs and domains were identified and appropriate questions for capturing these domains were constructed (see draft, **Appendix 6-7**). The quality steward surveys will assess site characteristics (RE-AIM) and colonoscopy protocols before and after VA-EQuIP implementation for use in assessing site level change after implementation. Practice changes include whether or not sites changed clinical protocols or practice, including quality measurement practices, quality reporting practices, bowel preparation protocols, endoscopy technique (e.g. withdrawal time), use of assist devices marketed to improve adenoma detection (e.g. cap), or seeking additional training or proctoring. The provider survey was modified from a previously developed, validated COM-B-based survey⁶⁹ to capture behavior change domains consistent with our conceptual model. Qualitative interviews with stewards will explore barriers and facilitators of VA-EQuIP implementation (RE-AIM QuEST).⁶⁹ Qualitative interviews with providers will explore components of behavior change related to VA-EQuIP implementation (**Appendix 8**).

Quantitative Survey Administration: The quantitative surveys will be delivered to the identified local quality stewards (N=73) and providers (N=657) for each enrolled site via the Research Electronic Data Capture (REDCap)⁷⁰ platform at baseline (prior to VA-EQuIP) and 12 months following completion of the VA-EQuIP intervention. We will incorporate established methods of maximizing web survey responses, including multiple, carefully-timed, integrated email contacts.⁷¹

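### The primary model's standard error leaves out site-by-quarter variation, and the robust fallback that would restore it depends on a check with no stated pooling or threshold

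*Combined protocol and SAP*

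**What the plan says.** All references are to Aim 1 of the combined protocol and SAP unless stated.

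- **Analysis Overview.** The primary analysis compares data before and after the intervention, within and across providers, while "controlling for secular trends, which are uniform across sites".
- **Primary Analysis -- Stepped Wedge at the Provider Level.** The outcome is the provider's monthly count, in a Poisson model with log link and an offset. On time: "We will additionally control for time since the study began in quarters (Time, coded as a categorical variable) to account for secular trends". On clustering: "Random effects will be included for both provider and site, where provider is nested within site". The equation ends with these two intercepts. It has no site-by-time term and no random intervention effect. Over-dispersion would lead to a negative binomial model.
- **Residual check, same section.** The team will "examine correlation between successive monthly ADR rates within providers using residual plots" and a Durbin-Watson type test. If the covariance departs substantially from the model, a GEE analysis with independence between sites and robust standard errors replaces it. No numerical trigger is given.
- **Power Calculation (stepped wedge).** "Based on an ADR of 27.5% in the pre-intervention period, we would have about 93% power to detect a 1.0% absolute increase in ADR". One ICC (0.030) is given, with no decay over time. The calculations "are conservative due to exclusion of three quarters of baseline data" and because clustering by provider is ignored.

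**The concern.** The intervention is assigned to whole sites, and the treatment contrast is made across site-quarters. If a site's ADR moves up and down over quarters for its own reasons, all its providers move together, and more exams in that quarter do not average the movement away. A model with constant intercepts and common quarter effects treats this movement as sampling noise of single exams. The standard error of the intervention effect is then smaller than it should be, relative to a correctly specified exam-level variance.

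At stake are the error rate of the primary test of a national program and the credibility of the stated power. The target effect is 1.0 percentage point, so site-level movement of one to two points per quarter is not negligible beside it.

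**Working it through.** **Inputs from the Power Calculation and design sections.** 69 sites, 571 providers and 135,517 patients per year, so n = 135,517/(4 × 69) = 491 exams per site-quarter and 135,517/(571 × 12) = 19.8 per provider-month; ADR 27.5% against 28.5%; ICC 0.03; six quarterly waves.

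**Assumed.** A two-sided 5% test, since the plan mentions only "their 95% confidence intervals (CIs), and p-values from the models"; and the CAC, the share of between-site variance that is constant over time, over a range.

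**1. Reproducing the stated power.** I used the generalized least squares variance for site-quarter means with categorical quarters. For each site, V = τ²·CAC·J + [τ²(1 − CAC) + σ²/n]·I, with σ² = 0.28 × 0.72 = 0.2016 and τ² = 0.2016 × 0.03/0.97 = 0.00624. Power = Φ(0.010/SE − 1.96). With one baseline quarter, six steps, four follow-up quarters, the implementation quarter counted as treated, and CAC = 1, SE = 0.00290 and power = Φ(1.49) = 93.2%. Using 95 providers per wave as clusters gives 93.4%. The stated 93% is therefore reproduced at CAC 1.

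**2. Type I error of the planned model.** At p = 0.275, the binomial variance of a site-quarter mean is p(1 − p)/n = 0.000406 (SD 2.0 points). The Poisson model uses p/n = 0.000560, which is 1/(1 − 0.275) = 1.38 times larger. Independent site-by-quarter variation adds s² = τ²(1 − CAC), with τ² = 0.1994 × 0.03/0.97 = 0.00617 at this rate. The between-site SD is large (7.9 points), so the estimate is almost wholly within site, and

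true SE / model SE = √[(0.000406 + s²)/0.000560], type I error = 2Φ(−1.96/ratio).

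At CAC 0.95, s² = 0.000308, the ratio is √(0.000714/0.000560) = 1.13, and the error is 8.3%. For binomial-size standard errors, the denominator is 0.000406.

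| CAC | Site-quarter SD (points) | SE ratio, Poisson | Type I, Poisson SE | Type I, binomial-size SE | Correctly sized power |
|---|---|---|---|---|---|
| 1.00 | 0 | 0.85 | 2.1% | 5.0% | 93% |
| 0.98 | 1.1 | 0.97 | 4.4% | 8.6% | 86% |
| 0.95 | 1.8 | 1.13 | 8.3% | 13.9% | 74% |
| 0.90 | 2.5 | 1.35 | 14.7% | 21.7% | 59% |

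The last column uses step 1 with SE = 0.00331, 0.00384 and 0.00459 for the lower three rows. The Poisson column crosses 5% where s² = p²/n, that is s = 0.275/√491 = 1.24 points.

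**3. Simulation under no effect.** 1,000 trials per setting: 69 sites, 14 quarters, implementation quarter dropped, binomial data, Poisson log-link fit, site fixed effects standing in for random intercepts.

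- Independent site-quarter SD of 0, 1.0, 1.25, 1.76 and 2.5 points: type I error 1.6%, 3.5%, 4.6%, 8.0% and 14.0%.
- Autocorrelated drift (first-order, 0.7), SD 1, 2 and 2.5 points: 4.5%, 12.8% and 18.9%.
- Purely linear site trends, SD of total change 3 to 10 points: 1.6% to 3.3%.
- Site-clustered robust standard errors: 4.1% to 6.7% in every setting.

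In two settings (independent 2.5 points, autocorrelated 2 points), at least one fit failed and was counted as a non-rejection.

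**4. Would the plan's safeguards respond?**

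- *Over-dispersion switch.* Provider-month variance is only 0.72 to 0.81 of the Poisson variance, even at CAC 0.80, so it would not be prompted.
- *Monthly correlation check.* At CAC 0.95, two months in the same quarter correlate at 0.000308/(0.000308 + 0.1994/19.8) = 0.030. Two of three successive pairs share a quarter, so the lag-1 correlation is about 0.02 (Durbin-Watson about 1.96). One provider with about 39 months has a standard error of 1/√39 = 0.16.
- *The same check pooled over providers.* In 400 simulated trials per setting (one-sided 5%), it detected an SD of 1.1, 1.7 and 2.4 points in 37%, 90% and 100% of trials. Tests of single providers rejected in only 6% to 8%.

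**The case against.** A reader might infer that ordinary site drift automatically narrows the interval and inflates the false-positive rate. The documents do not support that. They give no CAC or site-by-quarter variance, so what is ordinary cannot be read from them. The planned Poisson variance is too large for a 27.5% binary outcome and offsets drift up to about 1.25 points, and linear site trends do no harm in this design. All of this stands. However, the offset is a by-product of a misspecified variance: it would vanish if the variance were corrected, and it does nothing for the power statement.

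A reader might also infer that the GEE fallback could never be triggered. That holds for tests of one provider at a time. The plan does not exclude pooling, and a pooled check would usually detect the drift that matters. What remains is that neither pooling nor a threshold is stated, and a correlation of 0.02 could fairly be judged not substantial even when statistically detectable.

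Finally, a reader might take the Aim 2 survey items on "whether or not sites changed clinical protocols or practice, including quality measurement practices, quality reporting practices, bowel preparation protocols" as evidence that the plan expects background drift. That section (Quantitative Survey Design) concerns change after implementation, which is a route by which the intervention may work. The larger benefit expected in low-volume or low-ADR sites is effect heterogeneity, which the plan addresses through interaction terms and the secondary meta-regression. Those analyses do not change the primary standard error, but they make a random intervention effect in the primary model optional.

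**Conclusion.** The point holds in conditional form. The primary standard error omits irregular or autocorrelated site-by-quarter variation, and the plan assumes this away by taking secular trends as uniform. With the planned Poisson standard errors, type I error is about 2%, 4%, 8% and 15% at CAC 1.0, 0.98, 0.95 and 0.90. With binomial-size standard errors, it would be about 9%, 14% and 22% at the last three values. Power for 1.0 point is about 86%, 74% and 59% there, against the stated 93%.

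These figures rest on ICC 0.03, equal site sizes, a two-sided 5% test and an assumed CAC range. The SE ratios in step 2 do not depend on the layout, but the power figures do. They keep the implementation quarter as treated data, because only that reproduces 93%, whereas the design section discards that quarter. Discarding it gives 81% at CAC 1, 57% at 0.95 and 43% at 0.90 with one baseline quarter; that discrepancy is a separate matter.

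The two reasons given for calling the power conservative do not address the omitted variance, so the word is unsupported until a CAC is considered. Severity: should-fix. Confidence: moderate, because the structure is clear but the size of the variation is not documented.

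**What to change.** 1. **Primary Analysis and residual check.** Make site-clustered robust standard errors with a small-sample correction the default for primary inference, whatever the residual check shows. Alternatively, add a random site-by-quarter effect to the primary model. A random site-level intervention effect is optional.
2. **Analysis Overview.** Replace the statement that trends are uniform with an average secular trend plus site-specific deviations.
3. **Power Calculation.** Estimate the CAC from the 2018-2019 pre-intervention data, which the plan already uses for the strata and the baseline. Restate power over a range of CAC, and do not call it conservative without that.

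The cost is SAP wording and, for the second option in item 1, one variance component. The confidence interval would be somewhat wider and the stated power lower. No new data are needed.
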